9.10.3 Discontinued Participants Continuing to be Monitored in the Study

When a participant discontinues study treatment in the treatment or retreatment period, procedures for discontinuation will be performed.

The Discontinuation Visit should occur at the time study treatment is discontinued for any reason. If the Discontinuation Visit occurs 30 days from the last dose of study treatment, at the time of the mandatory Safety Follow-up Visit, the Discontinuation Visit procedures and any additional Safety Follow-up procedures should be performed. Visit requirements are outlined in Section 2 - Schedule of Activities. Additional details regarding participant withdrawal and discontinuation are presented in Section 8 -Discontinuation/Withdrawal Criteria.

9.10.3.1 Post-Study

Participants will be required to return to clinic approximately 30 days after the last dose of study treatment for the post-trial visit. If the post-trial visit occurs less than 30 days after the last dose of study treatment, a subsequent follow-up phone call should be made at 30 days post the last dose of study treatment to determine if any adverse events have occurred since the post-trial clinic visit

9.10.3.2 Safety Follow-up Visits

The mandatory Safety Follow-up Visit should be conducted approximately 30 days after the last dose of trial treatment or before the initiation of new anti-cancer treatment, whichever comes first. All AEs that occur prior to the Safety Follow-up Visit should be recorded. Participants with an AE of Grade >1 will be followed until the resolution of the AE to Grade 0-1 or until the beginning of a new anti-cancer therapy, whichever occurs first. SAEs that occur within 90 days of the end of treatment or before initiation of a new anti-cancer treatment should also be followed and recorded.

9.10.3.3 Imaging Follow-up Visits

Subjects who discontinue treatment for reasons other than verified PD should continue with imaging assessments per the protocol-defined schedule until: (1) PD is verified or further confirmed by the investigator, (2) initiation of a new anti-cancer treatment, (3) death, (4) withdrawal of consent, or (5) study conclusion or early termination, whichever occurs first.

9.10.3.4 Follow-up Visits

Participants who discontinue trial treatment for reasons other than disease progression will move into the Follow-up Phase and should be assessed Q9W by radiological imaging to monitor disease status. Every effort should be made to collect information regarding disease status until the start of a new anti-cancer therapy, disease progression, death, or the end of the study.

Information regarding post-study anti-cancer treatment will be collected if new treatment is initiated.

9.10.3.5 Survival Follow-up Contacts

Participant survival follow-up status will be assessed approximately Q12W until death, withdrawal of consent, or the end of the study, whichever occurs first.

The first survival follow-up assessment should be scheduled as described below:

- For participants who discontinue treatment intervention and who will not enter the efficacy follow-up phase, the first survival follow-up contact will be scheduled 12 weeks after the discontinuation visit and/or safety follow-up visit (whichever is last).
- For participants who completed assessments in the efficacy follow-up phase, the first survival follow-up contact will be scheduled 12 weeks after the last efficacy assessment follow-up visit has been performed.

9.10.4 Survival Status

To ensure current and complete survival data is available at the time of database locks, updated survival status may be requested during the course of the study by the Sponsor. For example, updated survival status may be requested prior to but not limited to an external Data Monitoring Committee (eDMC) review, interim and/or final analysis. Upon Sponsor notification, all participants who do not/will not have a scheduled study visit or study contact during the Sponsor defined time period will be contacted for their survival status (excluding participants that have a previously recorded death event in the collection tool).

10. Statistical Analysis Plan

This section outlines the statistical analysis strategies and procedures for the primary and secondary analyses of the study. Exploratory and other non-confirmatory analyses will be outlined in a separate sSAP.

If, after the study has begun, changes are made to primary and/or secondary objectives, or the statistical methods related to those objectives, then the protocol will be amended (consistent with ICH Guideline E9). Changes to exploratory or other non-confirmatory analyses made after the protocol has been finalized, but prior to the conduct of any analyses, will be documented in the sSAP as needed and referenced in the Clinical Study Report (CSR) for the study. Post hoc exploratory analyses will be clearly identified in the CSR.

10.1 Statistical Analysis Plan Summary

Trial Design Overview	A Phase 1b Multi-cohort Study of Pembrolizumab (MK-3475) in Combination With Binimetinib and/or Chemotherapy in Participants With Metastatic Colorectal Cancer (KEYNOTE-651)
Analysis Populations	Safety (Primary): All-Participants-as-Treated (APat) Efficacy (Secondary & Exploratory): Full Analysis Set (FAS)
Primary Endpoint(s)	Safety: Dose-limiting toxicities (DLTs)
Secondary Endpoints	ORR based on RECIST 1.1 as assessed by the investigator for each cohort.
Statistical Methods for Key Efficacy	The point estimate and 95% CI for ORR will be evaluated separately for each cohort, using exact binomial distribution.

Treatment Assignment	The trial is an open-label trial. Treatment allocation will be accomplished by non-random assignment. If a participant meets the eligibility criteria for Cohorts B and C (ie, previously untreated) or Cohorts D and E (ie, previously treated with one line of fluoropyrimidine-based therapy) then IVRS/IWRS will alternate assignments between the 2 cohorts with the same eligibility criteria. Treatment for each cohort in Part 2 will begin once a preliminary RP2D for that cohort is identified in Part 1.
Statistical Methods for Key Safety Analyses	Summary statistics (counts, percentages, means, standard deviations, etc.) will be provided for the safety endpoints as appropriate. The estimates of the DLT rates among participants treated at the RP2D and the 80% Bayesian credible intervals based on a prior distribution of Beta (1,1) for the estimates will be provided.
Interim Analyses	In this study, data will be examined on a continuous basis to allow for preliminary RP2D decisions (Part 1) and confirmation of RP2D (Part 2). Interim analyses will be conducted at the Sponsor's discretion to enable future trial planning. Futility analyses will be performed in the first 14 evaluable participants treated at the RP2D for each cohort.
Multiplicity	No multiplicity adjustment is planned.
Sample Size and Power	The actual sample size depends on the safety profiles and number of doses to be studied. A target sample size of 159 participants will be used for trial planning purposes.

10.2 Responsibility for Analyses/In-House Blinding

The statistical analyses of the data obtained from this study will be the responsibility of the Clinical Biostatistics department of the Sponsor.

The trial is open-label, ie, Participants, Investigators, and Sponsor personnel will be aware of participant treatment assignment after each participant is enrolled and treatment is assigned. Allocation to treatment will not be randomized.

10.3 Hypotheses/Estimation

Objectives and hypotheses of the study are stated in Section 4.

10.4 Analysis Endpoints

10.4.1 Efficacy Endpoints

Objective response rate is the secondary endpoint of the trial. Objective response rate is defined as the proportion of participants in the analysis population who experience CR or PR using RECIST 1.1 criteria as assessed by investigator review. Other efficacy endpoints (eg, DOR, DCR and PFS based on RECIST 1.1 as assessed by the investigator, ORR, DOR, DCR, and PFS based on iRECIST 1.1 as assessed by the investigator and OS) are exploratory endpoints in this trial and will be defined in the sSAP.

A description of efficacy assessments is provided in Section 9.2.

10.4.2 Safety Endpoints

The primary safety endpoint is the incidence of DLTs. Safety and tolerability will be assessed by clinical review throughout the trial. The toxicities and grades experienced by participants who have received study treatment, including AEs, SAEs and ECIs will be summarized. Other safety measures evaluated in study include laboratory tests, ECGs, ECHO/MUGA, vital signs, ECG measurements, physical examinations, and eye examination.

A description of safety measures is provided in Section 9.3.

10.5 Analysis Populations

10.5.1 Safety Analysis Population

The APaT population will be used for the analysis of safety data in this study. The APaT population consists of all participants who received at least 1 dose of study treatment for each cohort. In case of treatment administration errors, participants will be analyzed according to the treatment they actually received. For DLT evaluation, APaT who were observed for safety for 21 days (Cohort A) or 28 days (Cohorts B, C, D, and E) after the first dose of assigned treatment or experienced a DLT prior to 21 days (Cohort A) or 28 days (Cohort B, C, D, and E) after the first dose of assigned treatment will be used.

At least one laboratory or vital sign measurement obtained subsequent to at least 1 dose of study treatment is required for inclusion in the analysis of each specific parameter. To assess change from baseline, a baseline measurement is also required.

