5.1.1 Study Design

5.1.1.1 Part 1 (Dose Finding)

An mTPI design [Ji Y, Li Y, Bekele BN 2007] with a target DLT rate of approximately 30% will be applied to identify a preliminary RP2D in each cohort.

Dose escalation and de-escalation decisions are based on the mTPI design as outlined in [Table 1](#).

For **Cohort A**, the DLT observation period is the first **21-days** of Cycle 1 and the next dose level may open for enrollment once the 21-days DLT observation period of the previous dose is completed and a dose escalation decision is made.

For **Cohorts B, C, D, and E**, the DLT observation period is the first **28-days** to accommodate the chemotherapy schedule and the next dose level may open for enrollment once the 28-days DLT observation period of the previous dose is completed and a dose decision (escalation or de-escalation) is made.

During dose finding, a minimum of 3 participants are required at each dose level, and up to 6 participants may be enrolled in the same cycle at each new dose. In [Table 2](#), the columns indicate the numbers of participants treated at the current dose level, and the rows indicate the numbers of participants experiencing DLT. The entries in the table are the dose-finding decisions: E, S, D, and DU represent escalating the dose, staying at the same dose, de-escalating the dose, and excluding the dose from the trial due to unacceptable toxicity, respectively.

Based on the mTPI design, the number of participants who are enrolled at a dose but are not yet fully evaluable for DLT assessment may not exceed the number of remaining participants who are at risk of developing a DLT before the dose would be considered unacceptably toxic

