5.1.4 Replacement of Participants in DLT Period

[figure not shown]
To fully evaluate the safety of the combination therapy in this study, all participants enrolled must meet the criteria for evaluability during the DLT period. Participants are considered non-evaluable and will be replaced if:

- They are enrolled but not treated,
- They discontinue from the trial prior to completing all safety evaluations due to reasons other than drug-related AEs,
- They received <90% of the total pembrolizumab infusion during the DLT period (eg, because the infusion had to be discontinued due to an infusion reaction) and did not experience a drug-related event,
- They received <90% of the total SOC (mFOLFOX7 and FOLFIRI) infusion during the DLT period (eg, if the infusion had to be discontinued due to an infusion reaction) and did not experience a DLT,
- They received $\leq 75\%$ of binimetinib doses intended for the trial during the DLT period and did not experience a drug-related event,
- They must take a prohibited concomitant medication during the DLT period, unless this medication is used to treat a study drug-related AE,
- They must undergo medical/surgical procedures or have logistical issues not related to study therapy (eg, elective surgery, unrelated medical events) during the DLT period.

Non-evaluable participants will not be counted toward the cohort total for DLT evaluation.

Specific procedures to be performed during the trial, as well as their prescribed times and associated visit windows, are outlined in the Trial SoA - Section 2. Details of each procedure are provided in Section 9 – Study Assessments and Procedures.

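### Sections 10.5.1 and 5.1.4 define the DLT-evaluation set differently, so the reported primary DLT rate can differ from the one used for dose finding, and three 5.1.4 criteria can discard an observed DLT

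*Combined protocol and SAP*

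**What the plan says.** DLT incidence is the primary endpoint (Sections 10.1 and 10.4.2). Section 10.6.2 reports the DLT rate among participants treated at the RP2D, with an 80% credible interval from a Beta(1,1) prior.

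Section 10.5.1 defines the set for that purpose in two limbs, both restricted to treated participants:
- those observed for the full window: "For DLT evaluation, APaT who were observed for safety for 21 days (Cohort A) or 28 days (Cohorts B, C, D, and E");
- those with an earlier DLT: "or experienced a DLT prior to 21 days (Cohort A) or 28 days (Cohort B, C, D, and E").

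Section 5.1.4 lists seven grounds on which a participant is non-evaluable and replaced, and closes with "Non-evaluable participants will not be counted toward the cohort total for DLT evaluation". After the ground for untreated participants, the list has three exposure criteria: less than 90% of the pembrolizumab infusion, less than 90% of the chemotherapy infusion, and 75% or less "of binimetinib doses intended for the trial during the DLT period and did not experience a drug-related event". The other three are:
- leaving the trial: "They discontinue from the trial prior to completing all safety evaluations due to reasons other than drug-related AEs";
- prohibited medication: "They must take a prohibited concomitant medication during the DLT period, unless this medication is used to treat a study drug-related AE";
- an unrelated medical or surgical procedure, or a logistical problem, within the DLT window.

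Section 10.5.1 does not refer to 5.1.4. No visible text says which rule feeds the mTPI decisions and which feeds the 10.6.2 estimate.

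**The concern.** The set that selects the RP2D and the set that describes its toxicity should be the same, or the difference should be deliberate and stated. Here they can differ in two directions.

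1. **Extra DLT-free participants in the report.** Someone replaced for under-dosing but followed for 21 or 28 days satisfies the first limb of 10.5.1 and enters the denominator without a DLT. The reported rate falls; escalation is unaffected.
2. **A DLT missing from dose finding.** Someone with a DLT who also leaves the trial for an unrelated reason, needs a prohibited medication for something else, or has an unrelated procedure in the same window is, by the letter of 5.1.4, replaced and not counted. Section 10.5.1 counts that participant.

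The numbers are small: "a minimum of 3 participants are required at each dose level" (Section 5.1.1.1), with a cap of 14 (Section 10.9). One participant can therefore matter.

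**Working it through.** **Comparing the 5.1.4 grounds with 10.5.1**

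| 5.1.4 ground | Protects an observed DLT? | In the 10.5.1 set? |
|---|---|---|
| Not treated | No DLT possible | No |
| Leaves trial, reason other than a drug-related AE | No | Yes, if a DLT occurred or the window was completed |
| Pembrolizumab below 90% | Yes (requires no drug-related event) | Yes, if observed for the window |
| Chemotherapy below 90% | Yes (requires no DLT) | Yes, if observed for the window |
| Binimetinib 75% or less | Yes (requires no drug-related event) | Yes, if observed for the window |
| Prohibited medication | Only if it treats a drug-related AE | Yes, if observed or a DLT occurred |
| Unrelated procedure or logistics | No | Yes, if observed or a DLT occurred |

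A DLT must be judged at least possibly drug-related (Section 5.1.3), so requiring no drug-related event does protect DLTs. The three exposure criteria create direction 1. The three criteria without a full DLT exception create direction 2.

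**Effect on the reported rate**

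Inputs: cap of 14 (Section 10.9), Beta(1,1) prior and 80% interval (Section 10.6.2). The documents give no expected number of replacements, so the counts are assumptions. The posterior is Beta(1 + x, 1 + n − x), and the interval runs from its 10th to its 90th percentile.

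| Case | x/n | Rate | 80% interval |
|---|---|---|---|
| 5.1.4 set | 4/14 | 28.6% | 17.2–46.4% |
| One under-dosed, DLT-free participant added | 4/15 | 26.7% | 16.1–43.9% |
| Two added | 4/16 | 25.0% | 15.1–41.6% |
| One discarded DLT restored | 5/15 | 33.3% | 21.0–50.4% |
| Two added and one restored | 5/17 | 29.4% | 18.5–45.5% |

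The last row shows that the two effects can offset.

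**Effect on dose finding**

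Table 2 is redacted, so the mTPI settings are assumed: 30% target (Section 5.1.1.1), Beta(1,1) prior, symmetric margins around the target, and exclusion when P(rate > 0.30) exceeds 0.95. The action is the interval with the largest posterior probability per unit length.

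Check against the plan: Section 5.1.1.1 calls 4 DLTs in 6 unacceptably toxic. Here P(rate > 0.30 | 4/6) = 0.971, which exceeds 0.95, so the settings reproduce that example.

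Unit probability mass at a margin of 5 points:

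| x/n | Escalate | Stay | De-escalate | Action |
|---|---|---|---|---|
| 1/3 | 1.05 | 1.75 | 0.87 | Stay |
| 0/3 | 2.73 | 1.38 | 0.28 | Escalate |
| 2/6 | 0.97 | 2.24 | 0.82 | Stay |
| 1/5 | 1.86 | 2.15 | 0.49 | Stay |
| 1/6 | 2.22 | 2.11 | 0.36 | Escalate |

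These actions are the same at margins of 2, 3, 5, 8 and 10 points.

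- Dropping a DLT case alone does not change the action: 2/6 becomes 1/5 (still Stay), and 1/3 becomes 0/2, which is below the minimum of 3.
- If the replacement is DLT-free (probability 1 − 0.30 = 0.70 at a true rate of 30%), 1/3 becomes 0/3 and 2/6 becomes 1/6. Both move from Stay to Escalate.
- In the same way 4/6 (excluded) becomes 3/6, where P(rate > 0.30) = 0.874 and the action is Stay.

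The Stay-to-Escalate change matters only at DL1 of Cohorts A, C and E, because Cohorts B and D have no escalation step.

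**The case against.** Section 10 belongs to the same protocol, so 10.5.1 could be read as adding a time window to the 5.1.4 evaluability rule. That reading is reasonable for direction 1, but the text does not state it. It also does not settle direction 2, where 10.5.1 keeps a DLT that 5.1.4 removes.

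The affected groups may be small. Missing more than 25% of binimetinib because of drug-related AEs is itself a DLT (Section 5.1.3), so the binimetinib criterion catches only people under-dosed for other reasons. The chemotherapy criterion is wider, since it requires only the absence of a DLT. Direction 2 needs a DLT and an unrelated event in one window. This limits frequency but does not remove the conflict.

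Dose decisions are not mechanical. The totality of the data is considered before doses go to Part 2 (Section 5.1.1.1), safety data are reviewed before the next level opens (Section 5.1.2), and Part 1 DLTs are listed by dose level (Section 10.6.2). A discarded DLT would probably be seen. This softens the harm, but none of it says which denominator applies.

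The rate shifts are modest against an interval 29 points wide (46.4 − 17.2 = 29.2). The mTPI result also depends on the margins: with 10 points below and 5 above, 1/6 becomes Stay, so the 2/6-to-1/6 change disappears, while 1/3 to 0/3 remains Stay to Escalate. Both points stand as limits on size.

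**Conclusion.** The concern holds. The two sections give different memberships for the same evaluation. Followed as written, they can produce a primary DLT rate on a different set from the one that chose the RP2D.

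In the illustrations the reported rate moves from 28.6% to between 25.0% and 33.3%. A single discarded and replaced DLT can turn a Stay into an Escalate at the smallest sample sizes. The wording conflict is certain; its size is not. The numbers of affected participants, the mTPI margins and the exclusion cut-off are all assumed. The point should be fixed, but it does not undermine the design.

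**What to change.** Define one DLT-evaluable set and use it for both the mTPI decisions and the reported estimate: treated participants who either (a) had a DLT in the window, always counted, or (b) completed the window without a DLT and are evaluable under Section 5.1.4. Cite that set in Sections 10.5.1 and 10.6.2. In Section 5.1.4, add to the discontinuation, prohibited-medication and procedure/logistics criteria the condition that no DLT occurred, as the chemotherapy criterion already has.

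This changes protocol and SAP wording only. The reported rate may be slightly less favourable, because under-dosed participants without a DLT leave the denominator.

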10.5.2 Efficacy Analysis Population

The FAS population will be used for the analyses of efficacy data in this study. The FAS population consists of all evaluable participants for each cohort with a baseline scan with measurable disease by investigator assessment and received at least 1 dose of study treatment.

10.6 Statistical Methods

This section describes the statistical methods that address the primary and secondary objectives. Methods related to exploratory endpoints will be described in the sSAP.

10.6.1 Statistical Methods for Efficacy Analysis

Full Analysis Set population treated at RP2D in each cohort, the point estimate of ORR will be summarized along with a 95% CI using exact binomial method proposed by Clopper and Pearson (1934) [Clopper, C. J. and Pearson, E. S. 1934]. Statistical methods for other efficacy analyses will be documented in the sSAP.

10.6.2 Statistical Methods for Safety Analysis

Safety and tolerability will be assessed by clinical review of all relevant parameters including AEs, SAEs, ECIs, laboratory tests, vital signs, ECG measurements, and physical examinations.

[figure not shown]
Adverse events will be summarized by counts and frequencies for each dose level. Laboratory tests, vital signs, and other safety endpoints will be summarized as appropriate.

For Part 1 in each cohort: DLTs will be listed, and further summarized by dose level. The estimates of the DLT rates among participants treated at the RP2D and the 80% Bayesian credible intervals based on a prior distribution of Beta (1,1) for the estimates will be provided.

10.7 Interim Analyses

In this study, data will be examined on a continuous basis to allow for preliminary RP2D decisions (Part 1) and confirmation of RP2D (Part 2). Interim analyses will be conducted at the Sponsor's discretion to enable future trial planning.

CCI

10.8 Multiplicity

There will be no multiplicity control in this study.

10.9 Sample Size and Power Calculations

For each of the combinations, for Part 1 – dose finding phase: With sample size capped at 14 in each dose level, the maximum sample size in Part 1 is expected to be approximately 28 evaluable participants. In Part 2 – dose confirmation phase, approximately 16 additional participants per cohort will be treated at the RP2D identified in Part 1 to bring the total number of evaluable participants in Part 1 and Part 2 treated at RP2D to approximately 30 for each cohort. The actual sample size depends on the safety profiles and number of doses to be studied. A target sample size of 159 participants will be used for trial planning purposes. The key efficacy endpoint will be ORR based on the investigator assessment per RECIST 1.1. [Table 12](#) shows the ORR estimate and 95% CI (Clopper-Pearson interval) in each cohort.

Table 12 Estimate and 95% Confidence Interval of Objective Response Rate in Each Cohort

CCI

Abbreviations: CI=confidence interval; CR=complete response; ORR=objective response rate; PR=partial response.

